10.6.3 Vital Signs

Systolic and diastolic blood pressure and heart rate will be summarized for each treatment group using descriptive statistics at each scheduled visit.

10.6.4 Electrocardiogram (ECG)

For post-baseline assessments where ECG is performed in triplicate, the average of the 3 (or all available) readings will be used for analysis. Observations with the following diagnosis or findings will be excluded from analysis: artificial pacemaker, atrial

fibrillation, atrial flutter, left bundle branch block, and right bundle branch block. PR, QRS, QT, QTc and RR intervals and their change from baseline will be summarized for each treatment group by scheduled visit. In each treatment group, subjects will be categorized and summarized per their maximum post-baseline absolute QTc interval using limits of 450 ms, 480 ms, and 500 ms. They will also be categorized per their maximum change from baseline QTc interval using limits of 30 ms and 60 ms.

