7.7.5 Electrocardiograms

At each scheduled visit where ECGs are being obtained ECGs will be performed in a standardized method, in triplicate, and run consecutively (ie, < 30 seconds apart), prior to blood draws or other invasive procedures. Using equipment supplied to each site, all protocol-specified ECGs will be acquired and transmitted to the centralized ECG services provider. The Principal investigator (PI) or designated physician will review acquired ECGs. One (1) signed, original ECG tracing should be retained with the subject's source documents. At the request of the sponsor, the original ECG should be made available to Amgen to be manually read by a central reader.

The centralized ECG services cardiologists will perform standard interpretations of all tracings. A cardiologist reviewed ECG report will be provided to the study site.

Investigators must initial and date the ECG reports upon receipt. If the investigator's interpretation of any protocol-specified or unscheduled ECG differs from that supplied by centralized ECG services provider, it is the responsibility of the investigator to make the final clinical decisions. The investigator's interpretation does not need to be reconciled with that supplied by centralized ECG services cardiologists. Any clinical interventions based on these results need to be documented in the appropriate source documents and eCRF as applicable. It is the responsibility of the investigator to obtain additional

ECGs required for the clinical management of the subject, using centralized ECG services equipment or equipment on-site.

Further detail about the equipment provided and its use for this study will be provided in an Investigator ECG Manual distributed to the sites before start of enrollment.

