6.2 Demographics and Baseline Related Definitions

Age

Age at randomization will be derived in years in the clinical database.

Baseline Lipid and Lipid-related Parameters

Baseline values for fasting lipids (total cholesterol, HDL-C, LDL-C, VLDL-C and triglycerides), ApoA1, ApoB, hsCRP, Lp(a) and their derived parameters (eg, ratio between them) are defined as the mean of the two most recent non-missing fasting concentrations measured through central lab prior to or on Study Day 1. If for any reason only 1 value is available, then that value will be used as baseline.

BMI

Subject's BMI will be derived in kg/m² in the clinical database.

Other Baseline Values

For ECG, the baseline value is defined as the mean over all non-missing triplicate averages of 3 (or all available) readings from each set of triplicate taken prior to or on Study Day 1.

For ██████ the baseline value is defined as the average of the last two non-missing values collected prior to first IP administration. If for any reason only 1 value is available, then that value will be used as baseline.

For cIMT, the baseline value is defined as the non-missing value collected on or prior to study day 28.

For all other variables, the baseline value is defined as the last non-missing value collected prior to or on Study Day 1.

Change (absolute change) from Baseline

The arithmetic difference between a post-baseline value and baseline for a given time point:

Change (absolute change) from baseline = (post-baseline value – baseline value)

Percent Change from Baseline

The percent change from baseline for a given variable at a given time point is defined as:

100 x [(value at given time point – baseline value) / baseline value]

Baseline Metabolic Syndrome

For each subject without type 2 diabetes mellitus, metabolic syndrome is identified by the presence of 3 or more of the components listed below (modified AHA/NHLBI criteria, [Fryar et al 2012](#), [Ji et al 2010](#)). Subjects with type II diabetes cannot be categorized as having metabolic syndrome.

Age 10 to <16 years

Risk Factor	Defining Level
Elevated waist circumference:	Obesity \geq 90 percentile or adult cut-off if lower (refer to the cut-offs below)
Non-Asian (Fryar et al., 2012):	
Male:	
Age 10	\geq 85.6 cm
Age 11	\geq 90.4 cm
Age 12	\geq 93.7 cm
Age 13	\geq 96.7 cm
Age 14	\geq 101.3 cm
Age 15	\geq 99.9 cm
Female:	
Age 10	\geq 84.1 cm
Age 11	\geq 88 cm
Age 12	\geq 88 cm
Age 13	\geq 88 cm
Age 14	\geq 88 cm
Age 15	\geq 88 cm

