Appendix A. Analytical Study Week Assignments

Selected endpoints will be summarized by scheduled study visits in descriptive analyses. Since the actual visits may not exactly coincide with their scheduled visit day, the actual visit day is mapped to the study visit generally by non-overlapping consecutive intervals covering the entire time continuum. The mapping intervals for all distinct schedules are summarized in the following table:

Analytical Study week	Week 4	Week 8	Week 12	Week 16	Week 20	Week 22	Week 24
Scheduled Visit day	29	57	85	113	141	155	169
Vital Signs(sitting BP, HR)	(1,56]		(56,112]		(112,147]	(147,161]	(161,175]
Physical exam(including neurologic examination)							(1,175]
Body weight, waist circumference, Tanner staging, Body height							(1,175]
cIMT							(29,196]
Cogstate neurocognitive assessment							(1,175]
12 lead ECG			(1,126]				(126,175]
Fasting Lipids			(1,119]			(119,161]	(161,175]
Lp(a), ApoA1, ApoB			(1,119]			(119,161]	(161,175]
PK, █████			(1,119]			(119,161]	(161,175]
Chemistry, including fasting glucose			(1,126]				(126,175]
Hematology			(1,126]				(126,175]
Estradiol (females) / testosterone (males)							(1,175]
HbA1c, hsCRP, CK, FSH, LH, ACTH, DHEA-S, cortisol							(1,175]
Anti-evolocumab antibodies			(1,126]				(126,175]
HCV viral load							(1,175]
Urinalysis, urine microalbumin			(1,126]				(126,175]

Handling multiple records assigned to an analytical study week:

If there is more than one record in a study week interval, the analytical record for that specific study week will be defined as the record closest to the scheduled visit day of that specific study week ($7 \times \text{study week} + 1$). If two records are equidistant from the scheduled day, then the earlier record will be chosen. If there are multiple records on the same day, the last record will be used.

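### SAP 10.6.4 drops a new post-dose bundle branch block from the QRS summary, and no planned ECG output counts new block, atrial fibrillation or flutter by arm

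*SAP*

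**What the plan says.** SAP 10.6.4 is the whole ECG analysis plan in the readable text; Protocol 10.5.5 and 10.5.6 contain no ECG analysis. It has four elements.

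- Averaging: "For post-baseline assessments where ECG is performed in triplicate, the average of the 3 (or all available) readings will be used for analysis".
- Exclusion: "Observations with the following diagnosis or findings will be excluded from analysis: artificial pacemaker, atrial", continuing "fibrillation, atrial flutter, left bundle branch block, and right bundle branch block".
- Interval summaries: "PR, QRS, QT, QTc and RR intervals and their change from baseline will be summarized for each treatment group by scheduled visit".
- QTc categories: maximum post-baseline QTc against 450, 480 and 500 ms, and then "They will also be categorized per their maximum change from baseline QTc interval using limits of 30 ms and 60 ms".

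SAP 6.2 sets the baseline: "For ECG, the baseline value is defined as the mean over all non-missing triplicate averages", using sets taken up to and including Study Day 1. It says nothing about subjects who already have one of the listed findings.

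Protocol 7.7.5 provides the diagnostic reads: "The centralized ECG services cardiologists will perform standard interpretations of all tracings". The same section says that the investigator's interpretation does not have to be reconciled with the central one.

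**The concern.** The rule selects observations on something that can happen after randomisation. For QT and QTc this is a familiar choice, because these conditions distort the measurement. For QRS it is different: bundle branch block is a widening of the QRS complex, so the excluded finding is the abnormality that the interval measures. If treatment caused such a change, the affected values would leave the QRS summary and the comparison between arms would move toward no difference.

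The second gap is that nothing in the ECG plan counts these diagnoses. The SAP gives worst-shift tables and threshold incidences for laboratory values (10.6.2), and incidence overall and by exam area for neurologic findings (10.6.5). ECG diagnoses have no counterpart, although every tracing is read centrally.

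**Working it through.** The documents give no figure for this point, so the check is a reading of the text followed by an illustration.

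**1. Does the rule cover post-baseline tracings?** Yes. The sentence before it concerns post-baseline assessments, and the rule itself has no time limit.

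**2. Does it cover more than QT and QTc?** Yes. The sentence after it names PR, QRS, QT, QTc and RR, and no interval is exempted.

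**3. Follow one child.** Suppose the Day 1 ECG is normal and right bundle branch block is present on every reading at weeks 12 and 24, the only scheduled post-baseline ECGs (Protocol Table 1). The baseline stays valid. Both post-baseline averages are excluded, so the child contributes no QRS change. If instead an observation is a single tracing and only some of a triplicate is affected, the remaining readings are averaged and the visit is kept.

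**4. Could another planned output show the finding?**

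| Output | Shows a new block, atrial fibrillation or flutter? |
|---|---|
| Interval summaries (SAP 10.6.4) | No, excluded |
| QTc categories (SAP 10.6.4) | No, excluded |
| Number of subjects per summary (SAP 10.1) | Falls, but an exclusion looks the same as a missed ECG |
| Heart rate from vital signs (SAP 10.6.3) | Rate only, not the diagnosis |
| Treatment-emergent adverse event tables (SAP 10.6.1) | Only if the investigator reports it |
| Table of new ECG diagnoses, or count of exclusions | Not planned |

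The exploratory sections are redacted in both documents, so this covers the readable text only.

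**5. Illustration for QRS.** The 100 evolocumab subjects come from SAP 3.2. The incidence p of new bundle branch block and the widening D are assumptions; neither is in the documents. Other subjects are taken to have no change, and each block to be present on all readings at the visit.

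- Mean QRS change with all values kept = p × D.
- Mean QRS change under the rule = 0, because only unchanged subjects remain.
- Chance of at least one such subject = 1 − (1 − p)^100.

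| p | Mean change kept, D = 20 to 60 ms | Under the rule | Chance of at least one in 100 |
|---|---|---|---|
| 1% | 0.2 to 0.6 ms | 0 ms | 1 − 0.99^100 = 63% |
| 2% | 0.4 to 1.2 ms | 0 ms | 1 − 0.98^100 = 87% |
| 5% | 1.0 to 3.0 ms | 0 ms | 1 − 0.95^100 = 99% |

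The means move little. SAP 10.1 also calls for minimum and maximum values. One retained child with a 60 ms increase would put the maximum change at 60 ms or more; under the rule that value is gone.

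**The case against.** The strongest reply is that incidence of cardiac events belongs to adverse event reporting, which the ECG exclusion does not touch. The investigator or a designated physician reviews the tracings, receives the cardiologist's report and must initial and date it. The adverse event definition in Protocol 9.1.1 is broad and needs no causal link. The carve-out in 9.2.1 for abnormal findings without clinical significance is written for laboratory results. An independent committee also reviews accumulating data. ECG is not among the readable safety endpoints, its analysis is descriptive, and a mean QRS would hardly reveal a few blocks anyway.

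Much of this stands, and it rules out several stronger readings that a reader might infer:

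- *That the tables would report zero incidence in place of the true rate.* No incidence table for these diagnoses is planned, so no rate is replaced by zero.
- *That the safety report would look normal however many children were affected.* Reported events still reach the adverse event tables; only the ECG summaries lose them.
- *That PR and RR suffer as QRS does.* PR cannot be measured in atrial fibrillation or flutter. A mean RR would not identify either rhythm, and heart rate is summarised separately without this exclusion.
- *That every new block removes all of a child's post-baseline ECG data.* That needs all readings at both visits to be affected.

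The reply does not close the gap. Because the two readings need not be reconciled, a centrally read new block that the investigator does not record as an adverse event would be absent from both the interval tables and the adverse event tables.

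**Conclusion.** The point holds, with QRS and bundle branch block at its centre. As written, the rule removes a new post-dose block from the QRS summary, and no planned ECG output in the readable text counts new block, atrial fibrillation or flutter by arm. The adverse event tables are a real but incomplete backstop.

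The practical size is probably small: few events are expected, and the assumed cases above shift the mean QRS change by 0.2 to 3.0 ms. The main loss is the by-arm count of affected children. No efficacy result or planned hypothesis test is affected.

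The conclusion rests on taking the exclusion sentence as written, without an unstated limit to baseline findings or to QT/QTc.

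**What to change.** In SAP 10.6.4:

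1. Limit the exclusion to QT and QTc, or to findings already present at baseline, so that QRS values with new bundle branch block are kept. The second option would also keep new-block tracings in QTc, so state which is meant. Say whether an observation is one tracing or the triplicate average.
2. Add a by-arm table of new post-baseline left bundle branch block, right bundle branch block, atrial fibrillation and atrial flutter from the central reads, in subjects without that finding at baseline.
3. Report the number of observations excluded per arm and visit.

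The cost is SAP wording and one small table from reads that the protocol already requires; no visit or procedure is added. The downside is a somewhat larger QRS standard deviation if such values occur, which should be slight if they are as rare as expected.

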10.6.5 Neurologic Examination

The incidence of abnormal neurologic findings overall and in each exam area will be summarized by treatment group.

10.6.6 Cogstate Neurocognitive Assessment

For each test, the change from baseline to EOS in the standardized score will be summarized by treatment group.

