2.4 Rationale

FH is a genetic disorder which typically requires lifelong treatment, sometimes beginning in childhood. It is therefore important to study the safety and efficacy of potential treatments for FH in children and adolescents. Because developmental processes that are complete in adults are ongoing in children and adolescents, additional safety assessments (eg, biochemical and clinical assessments of puberty, carotid intimal medial thickness, and cognition) are also appropriate. Data from a dedicated randomized placebo-controlled study of evolocumab and adolescents will support the existing data from nonclinical studies in ages corresponding to human adolescence and clinical data from adolescent subjects participating in the TESLA and TAUSSIG studies.

The safety and efficacy of evolocumab 420 mg SC QM in adults have been extensively studied in phase 2 and phase 3 clinical trials. Additionally, in the two studies that have included pediatric subjects (TESLA and TAUSSIG), evolocumab lowered LDL-C and other lipid parameters in subjects aged 12-17 years. The percent change from baseline in LDL-C has been chosen as the primary assessment for this study because of the extensive body of data from interventional studies and epidemiological evidence demonstrating a strong causal relationship between serum LDL cholesterol, and the risk of CHD. These data also support the relationship with other clinical manifestations of atherosclerosis such as cerebrovascular disease (stroke) or peripheral vascular disease. These relationships are present over a broad range of LDL-C levels. Additionally, current guidelines focus on LDL-C as a target for therapy.

Non-HDL cholesterol (non-HDL-C), ApoB, the ratio of total cholesterol/HDL-C, the ratio of ApoB/ApoA1, and Lp(a) have been included as secondary efficacy endpoints because these markers are known as useful markers of cardiovascular risk under certain circumstances and because they may be employed as future targets for lipid lowering therapy.

Additional endpoints include triglycerides and HDL-C because data in adults demonstrates lowering of triglycerides and raising of HDL-C with evolocumab. In addition, triglycerides and HDL-C are independent risk factors for cardiovascular disease ([Austin et al, 1998](#); [Sarwar et al, 2007](#)).

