7.7.7 Neurocognitive Assessments

The Cogstate cognitive battery is a set of neuropsychological tests administered to subjects via computer. In Study 20120123, the battery will consist of the following 4 tests:

- **Groton Maze Learning Task (GMLT; Executive Function):** The Groton Maze Learning task is a measure of problem solving and reasoning and uses a well-validated maze learning paradigm. In this task, the subject is shown a 10 x 10 grid of boxes on a computer screen. A 28-step pathway is hidden among these 100 possible locations. Each box represents move locations, and the grid refers to the box array (ie, 10 × 10). Subjects are required to find the hidden pathway guided by 4 search rules. These rules are: do not move diagonally, do not move more than 1 box (ie, do not jump), do not move back on the pathway, and return to the last correct location after an error. At each step, only the most recently selected box is shown. Feedback is given with visual and auditory cues (green check marks and red crosses) to indicate whether the selected box is correct or incorrect. The head of path, or the last correct location, flashes with a green check when two errors are made in succession (failing to return errors). There are 20 well-matched alternate pathways available. The software records each move as an error or as a correct move.
- **One Card Learning Test (OCL; Visual Memory):** The One Card Learning test is a measure of visual recognition memory and uses a well-validated pattern separation paradigm using card stimuli. In this test, the cards are similar to those found in a deck of playing cards. The subject is asked whether the card currently being presented in the center of the screen was seen previously in this test. The subject responds by pressing the Yes or No key. Because no card has been presented yet, the first response is always No.

- Identification Test (IDN; Attention/Vigilance): The Identification test is a measure of visual attention and uses a well-validated choice reaction time paradigm using card stimuli. In this test, the playing cards are all either red or black. The subject is asked whether the card currently being presented in the center of the screen is red. The subject responds by pressing the Yes key when the card is red and No when it is black.

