- Detection Test (DET; Psychomotor Speed): The Detection test is a measure of information processing speed and uses a well-validated simple reaction time paradigm using card stimuli. In this test, the playing cards are all red and black. The subject is asked to press the Yes key as soon as the card in the center of the screen flips over.

This battery will be administered 3 times during the study: during screening, on study Day 1 (baseline), and at Week 24 (EOS). Completion of this test battery will take approximately 15 to 20 minutes at each administration. The Cogstate tests do not require complex language skills for administration, and the forms themselves do not use linguistic stimuli or responses.

Cogstate tests have been used to examine the potential adverse effects of mobile telephone use in young adolescents ([Abramson et al, 2009](#)), adolescents with eating disorders ([Allen et al, 2013](#)), skipping breakfast in elementary schoolchildren ([Kral et al, 2012](#)), dietary patterns in adolescents ([Nyaradi et al, 2014](#)), and in utero exposure to cocaine ([Mayes et al, 2007](#)). The Cogstate tests have also been used to examine the cognitive effects of treatment with stimulant medication in children with attention deficit hyperactivity disorder (ADHD) ([\[Mollica et al, 2004\]](#): 8 to 12 year olds; [\[Snyder et al, 2008\]](#): 6 to 16 year olds), as well as the effects of computerized cognitive rehabilitation in pediatric cerebral malaria survivors as young as 5 years old [\[Bangirana et al, 2009\]](#).

Additionally, regulatory authorities have approved the use of Cogstate tests for monitoring and evaluating the safety of central nervous system penetrant drugs in a range of pediatric indications, including epilepsy, neurogenic detrusor over-activity, bipolar depression, schizophrenia, and hyponatremia, and in children as young as 4 years old. In sports, Cogstate tests are being used to make return-to-play decisions in suspected concussion.

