2.3 Secondary Safety

- to evaluate the safety of SC evolocumab compared with placebo, when added to standard of care, in pediatric subjects 10 to 17 years of age with HeFH

[figure not shown]

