4.1.7 Other Safety Endpoints

- Change from baseline score in the components of the Cogstate battery at each scheduled administration

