10.1 General Principles

The final analysis will be conducted when all subjects have either completed all the scheduled study visits or have early terminated from the study. At that time, the database will be cleaned, processed and a snapshot will be taken; the study will also be unblinded. Based on the snapshot, efficacy and safety analyses will be performed on the FAS. Unless specified otherwise, the FAS will be the default analysis set in this study and data will be summarized by randomized treatment group. The superiority of evolocumab to placebo will be assessed for all efficacy endpoints.

Subject disposition, demographics, baseline characteristics, and exposure to IP will be summarized.

Summary statistics for continuous variables will include the number of subjects, mean, median, standard deviation or standard error, minimum, and maximum. For categorical variables, the frequency and percentage will be summarized.

Methods of handling missing data for efficacy endpoints will be described throughout this section. Missing data will not be imputed for safety endpoints.

Multiplicity Adjustment Method

In order to preserve the familywise error rate at 0.05, multiplicity adjustment for the multiple endpoints (**primary efficacy endpoint: percent change from baseline to week 24 in LDL-C and secondary efficacy endpoints: mean percent change from**

baseline to weeks 22 and 24 in LDL-C, change from baseline to week 24 in LDL-C and percent change from baseline to week 24 in non-HDL-C, ApoB, total cholesterol/HDL-C ratio and ApoB/ApoA1 ratio) will be performed using sequential gatekeeping and Hochberg procedures (Hochberg, 1988) as follows:

1. If the treatment effect from the primary analysis of the primary endpoint is significant at a significance level of 0.05, statistical testing of the **mean percent change from baseline to weeks 22 and 24 in LDL-C and change from baseline to week 24 in LDL-C** will proceed using the sequential procedure with a significance level of 0.05 (ie, **change from baseline to week 24 in LDL-C** will be tested only if **mean percent change from baseline to weeks 22 and 24 in LDL-C** is statistically significant at 0.05 significance level).

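### Cogstate change is to be summarised only within each arm; a planned baseline-adjusted difference from placebo with a 95% interval would be a cheap improvement

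*SAP*

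**What the plan says.** Protocol 7.7.7 states that "the battery will consist of the following 4 tests": executive function, visual memory, attention and psychomotor speed. They are given at screening, on Day 1 and at week 24, so there is one post-baseline score per child.

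The only item under Other Safety Endpoints (SAP 4.1.7, Protocol 10.1.1.7) is "Change from baseline score in the components of the Cogstate battery at each scheduled administration". Protocol 7.7.7 labels Day 1 as baseline. The SAP 6.2 rule agrees: "For all other variables, the baseline value is defined as the last non-missing value collected prior to or on Study Day 1".

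The whole analysis is one sentence in SAP 10.6.6, identical in Protocol 10.5.6: "For each test, the change from baseline to EOS in the standardized score will be summarized by treatment group". SAP 10.1 fixes what such a summary holds: "Summary statistics for continuous variables will include the number of subjects, mean, median, standard deviation or standard error, minimum, and maximum". That list has no between-arm difference, confidence interval or covariate. The superiority assessment in SAP 10.1 and the repeated measures model in SAP 10.5 apply to efficacy endpoints, and no other section adds a Cogstate contrast.

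The safety objective (SAP 2.3, Protocol 1.3) is nevertheless "to evaluate the safety of SC evolocumab compared with placebo, when added to standard of care".

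**The concern.** The objective asks for a comparison and the planned output stops one step short of it. This matters more for Cogstate than for a routine laboratory value. Protocol 2.4 explains why extra assessments are included: "Because developmental processes that are complete in adults are ongoing in children and adolescents, additional safety assessments" are called for, and cognition is one of its examples. Maturation over 24 weeks and repeated exposure to the tests could both move scores. This is an inference, since the documents quantify neither. Randomised placebo controls for both, so the difference from placebo is the quantity to interpret.

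The documents state no SD, margin, power or precision for Cogstate. If two arm means look alike in a table, the report could call that reassuring without showing how large an effect remains compatible with the data. A planned estimate with an interval would show it.

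**Working it through.** **The plan's own figure.** The only stated power, approximately 99%, is for LDL-C (SAP 3.2): a 40-point effect, SD 20, 100 vs 50 randomised and 20% discontinuing. With 80 vs 40, the standardised effect is 40 / (20 x sqrt(1/80 + 1/40)) = 40 / (20 x 0.1936) = 10.3, and power exceeds 99.99%. The stated figure is therefore conservative, but it says nothing about Cogstate.

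**What the planned table already allows.** With n, mean and SD (or SE) of change per arm, the unadjusted difference is mean_e - mean_p, and its 95% interval is that difference ± t x sqrt(SD_e²/n_e + SD_p²/n_p). An adjusted estimate also needs the baseline means and the baseline-to-week-24 covariance, or subject-level data for the strata. A summary of change alone does not give these.

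**Precision, unadjusted and adjusted.** Inputs:

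- Sample sizes are 100 vs 50 (SAP 3.2). The second case, 80 vs 40, assumes that 20% of each arm lack a week 24 score.
- The SD of the score is set to 1 at both times, because the documents give no SD and do not define how the score is standardised.
- The Day 1 to week 24 correlation r is assumed to be 0.5, 0.7 or 0.9, because the documents give none.

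Formulas:

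- Half-width = t x SD x sqrt(1/n_e + 1/n_p), with t about 1.98.
- SD of raw change = sqrt(2(1 - r)): 1.000, 0.775 and 0.447.
- Residual SD after baseline adjustment = sqrt(1 - r²): 0.866, 0.714 and 0.436.
- Ratio of the two = sqrt((1 + r)/2): 0.866, 0.922 and 0.975.

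The multiplier sqrt(1/n_e + 1/n_p) is 0.1732 for 100 vs 50 and 0.1936 for 80 vs 40.

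| r | 100 vs 50: change to ANCOVA | 80 vs 40: change to ANCOVA | Interval narrower by |
|---|---|---|---|
| 0.5 | 0.34 to 0.30 | 0.38 to 0.33 | 13% |
| 0.7 | 0.27 to 0.24 | 0.30 to 0.27 | 8% |
| 0.9 | 0.153 to 0.149 | 0.171 to 0.167 | 2.5% |

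**Why two similar arm means are weak evidence.** In units of the SD of change, an unadjusted comparison has power of 41% (100 vs 50) or 34% (80 vs 40) for a true difference of 0.3. The difference detectable with 80% power is (1.96 + 0.84) x 0.1732 = 0.49, or 0.54 with 80 vs 40. No test is being proposed. These figures only show that a table without an interval can hide a moderate difference.

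**The case against.** The strongest objection is that this is largely a matter of reporting style. Laboratory values, vital signs, ECG, neurologic examination and antibodies are all summarised descriptively in SAP 10.6. Cogstate ranks below the secondary safety endpoints and has no hypothesis or margin. Potential neurocognitive events (SAP 10.6.1), the neurologic examination (SAP 10.6.5) and the data monitoring committee also cover the area. The summary is by treatment group beside a concurrent blinded placebo arm, so neither arm is read in isolation. The screening run makes Day 1 the second exposure to the battery, which may reduce practice drift. With no margin, an interval of about 0.3 SD does not itself establish safety. All of this stands, and it limits the weight of the point. It does not supply the comparison that the objective calls for.

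Four stronger readings are tempting, and the documents do not support them:

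- **The report could not show what effect is excluded.** An unadjusted interval can be rebuilt from the planned n, mean and SD or SE. What is missing is the planned estimate and the adjusted interval.
- **Change scores ignore the baseline.** They subtract it, with the slope fixed at 1. ANCOVA estimates the slope instead.
- **Age is ignored.** Randomisation is stratified by age, and the undefined standardised score may already be age-normed. If so, the age covariate adds less.
- **One fifth of the children will lack week 24 data.** The 20% in SAP 3.2 is discontinuation of investigational product. Those subjects are asked to keep attending (Protocol Synopsis, Procedures; Protocol 6.2.2), so 80 vs 40 is a cautious scenario only.

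**Conclusion.** The point holds as a cheap improvement. Neither document plans an evolocumab-minus-placebo Cogstate estimate or interval, although the safety objective is comparative and the protocol names cognition as an additional assessment for this age group. That gap does not depend on any assumption.

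The lost precision is secondary. Its size rests on an assumed correlation and on equal SDs at the two times: about 13% of the interval width at 0.5, but only 2.5% at 0.9. A reader might infer that raw change wastes substantial information. The documents give no correlation from which to conclude that, and at high correlation the loss is negligible. The primary efficacy conclusion and the familywise error rate are unaffected.

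**What to change.** In SAP 10.6.6, keep the descriptive summary. Add, for each of the four tests, the evolocumab-minus-placebo difference in week 24 score with a 95% CI from an ANCOVA with treatment, the Day 1 score (baseline as in SAP 6.2) and the randomisation strata (age and screening LDL-C) as covariates. Modelling change with the same covariates gives the same treatment difference, so the endpoint definition need not change. State that this is estimation only, with no p-value and no change to the multiplicity scheme.

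The cost is four model outputs, and all the data are already collected. The downside is four safety intervals without multiplicity adjustment, which need cautious reading. The SAP should say so.
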